NCT02994979

Title: "Multicomponent Intervention to Prevent Delirium in Nursing Homes"

Principal Investigator: [name]

Date of document: 11/11/2014

A. SIGNIFICANCE

A.1 Importance of delirium in nursing home patients

Delirium is frequent and adversely affects quality of life in older adults. Approximately one third of older adults hospitalized with acute medical problems experience delirium.^{1, 25-26} Delirium in nursing homes, as in hospital settings, is often precipitated by acute illness. Nursing home residents experience 2-4 acute illness episodes per year (e.g., respiratory, urinary tract, and gastrointestinal infections),²⁷⁻²⁸ and ¾ of these are managed in the nursing home. Studies show a delirium prevalence of 16-23% at the time of nursing home admission³⁻⁴ and up to 33% in nursing home long-term care,⁵⁻⁶ and a nearly universal presence of multiple delirium risk factors (one or more of: cognitive impairment, immobility, sensory impairment, and neuropsychiatric medication use).⁷⁻¹⁰ Delirium is reported to be an uncomfortable and traumatic experience by those who have experienced it – with acute distractibility, disorientation, hallucinations, and change in alertness – and for family witnesses.²⁹ In longitudinal studies of delirious nursing home patients these symptoms last for 1-9 weeks in those whose delirium remits, but 20% of delirious nursing home patients remain symptomatic past 24 weeks of follow-up.³⁰ Many nursing home patients who develop delirium do not return to their pre-delirium level of cognitive function.¹¹ Delirium in nursing home patients is a powerful risk factor for poor health outcomes. As compared to those without delirium, patients with delirium are more likely to die,⁵ be hospitalized or rehospitalized,¹² and less likely to be discharged home.¹² These adverse outcomes parallel the outcomes of hospitalized older adults with delirium, who have longer hospital stays, 2-3 fold higher mortality at 1 year, and increased risk of nursing home stays.³¹ Cognitive change indicative of delirium is a common reason for hospital transfer of nursing home patients.¹³⁻¹⁴ The association of delirium with increased hospital use drives excess costs, with total 1-year excess costs attributable to delirium between \$18,024 - \$71,221 per patient in 2014 dollars.¹⁵

A.2 Lack of existing approaches to delirium in the long-term care setting

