C.6 Power and effect size. Based on our previous studies and the known impact of HELP on delirium,¹⁹ we hypothesize observing a clinically meaningful 40-60% relative reduction in new delirium from 35% to between 15% and 20%. Power calculations have been performed treating delirium as a binary (CAM) and continuous (DI) outcome and accounting for clustering of observations by unit and for correlations over time. For the binary variable, new delirium is defined as when delirium occurs any time during the illness period. Sample size was calculated (Figure 1) with the continuity correction,⁷²⁻⁷³ with assumed reliability (R)=.72; groups (g)=2; cluster size (by unit)=18; intraclass correlation (ICC)=.01; and variance inflation factor (VIF)=1+(cluster size-1)*ICC=1.17. With $\alpha=.05$ and ρ (estimated average correlation of the outcome measures over time)=0.60, a sample size of 150 per group will provide 80% power to detect a group difference in new delirium from 35% (baseline)

$$\text{Figure 1. } n' = \frac{(z_{\alpha/2} \sqrt{2P\bar{Q}} + z_{\beta} \sqrt{P_1Q_1 + P_2Q_2})^2}{(P_2 - P_1)^2}; n = \frac{n'}{4} \left(1 + \sqrt{1 + \frac{4}{n'(P_2 - P_1)}} \right)^2, \text{ where } \bar{p} = \frac{1}{2}(p_1 + p_2) \text{ and } \bar{q} = 1 - \bar{p}$$

to 18% (intervention). If the usual care group also has a small reduction in delirium to 30%, with 150 per group it will be possible to detect a reduction to 13.5% in the intervention group, a 55% relative reduction. Thus, 150 subjects per intervention group will provide sufficient power to detect the hypothesized difference between groups. Power was also examined using the sample size formula for the log-rank test. Assuming a VIF of 117%, $\alpha=.05$, and $\rho=.60$, given the same scenarios as above, with a sample size of 150 per group and power 80%, the detectable λ (hazard ratio) is 2.9. For the continuous

measure (DI), power calculations are based on an assumed σ (population pooled standard deviation) of 3.12, using data from our previous study. The effect size estimate is: δ (DI group difference) and $d = \delta/\sigma$ (where d is Cohen's d). Adjusting for clustering and reliability, the detectable endpoint difference with

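### At a 30% usual-care rate, section C.6 reaches 80% power only for a relative reduction of about 53-55%, so its unqualified claim of sufficient power does not cover the lower part of the hypothesised 40-60% range

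*Combined protocol and SAP*

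**What the plan says.** All the relevant text is in C.6 (Power and effect size). The hypothesis reads: "we hypothesize observing a clinically meaningful 40-60% relative reduction in new delirium from 35% to between 15% and 20" per cent. With 150 per group, two-sided alpha of .05 and a continuity-corrected formula (Figure 1), C.6 claims 80% power for 35% vs 18%. It lists reliability R=.72, a variance inflation factor (VIF) of 1.17 and an over-time correlation of 0.60, but does not show how R and the correlation enter the binary calculation.

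C.6 then lets usual care fall to 30% and says that "with 150 per group it will be possible to detect a reduction to 13.5% in the intervention group, a 55% relative reduction". The next sentence concludes: "Thus, 150 subjects per intervention group will provide sufficient power to detect the hypothesized difference between groups". No power is given for any other intervention rate against a 30% control.

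**The concern.** The 30% scenario is offered as a robustness check, but it reports only the effect that keeps power at 80%. It does not report power for the effects that were hypothesised. Applied to a 30% control, a 40-60% relative reduction means intervention rates of 18% down to 12%. C.6's detectable rate of 13.5% is towards the low end of that span, so most of the span (13.5% to 18%) has less than 80% power. It is also below the 15-20% rates that C.6 names for a 35% start.

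This matters because new delirium is the binary outcome of the Aim 1 primary analysis (C.7), and C.9 says that a finding of no effect would also be important. A reader who relies on the C.6 conclusion could take a null result as evidence against a 40-50% reduction that the trial had only a moderate chance of detecting.

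**Working it through.** **Inputs (all from C.6).** Two-sided alpha .05 (z = 1.960); 80% power (z = 0.842); 150 per group; cluster size 18 and ICC .01, so VIF = 1 + 17 × .01 = 1.17; R = .72; continuity correction as in Figure 1.

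**Formula.** With P̄ = (P1+P2)/2 and d = |P1−P2|:

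n′ = [1.960·√(2P̄Q̄) + 0.842·√(P1Q1+P2Q2)]² / d²; n = (n′/4)·[1+√(1+4/(n′d))]².

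**Step 1: n per group before any inflation, at 80% power.**

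- 35% vs 18%: P̄ = .265; n′ = (1.960×.6241 + .842×.6125)²/.17² = 104.6; n = 116.1.
- 30% vs 13.5%: P̄ = .2175; n′ = (1.960×.5834 + .842×.5716)²/.165² = 96.9; n = 108.7.
- 30% vs 15%: n = 133.5.
- 30% vs 18%: n = 214.0.

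**Step 2: reproduce the plan's figures.** To turn 116.1 into 150 needs an inflation factor of 150/116.1 = 1.29. To turn 108.7 into 150 needs 150/108.7 = 1.38. Both lie between VIF alone (1.17) and VIF/R (1.17/.72 = 1.625). For 30% vs 13.5%, VIF/√R = 1.379 gives 149.9 and 1/R gives 151.0, so the 13.5% figure reproduces. For 35% vs 18%, VIF/R × (1+ρ)/2 = 1.30 gives 150.9. No factor tried gives both printed pairs within 3%. If 18% is a rounding of 17.5%, VIF/√R gives both. The adjustment is therefore unknown, and the results below are shown as a range.

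**Step 3: power at a 30% control.** The same formula is solved for power at effective n = 150/factor.

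| Reading | Effective n | 12% (60% reduction) | 15% (50%) | 18% (40%) | Rate with 80% power |
|---|---|---|---|---|---|
| Matched to 35% vs 18% | 116.1 | 90% | 74% | 51% | 14.0% |
| Matched to 30% vs 13.5% | 108.7 | 88% | 70% | 48% | 13.5% |
| VIF only | 128.2 | 93% | 78% | 56% | 14.7% |
| VIF and R | 92.3 | 81% | 62% | 41% | 12.2% |

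On the two readings that match C.6, 80% power needs a relative reduction of 1 − 14.0/30 = 53% to 1 − 13.5/30 = 55%.

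**Step 4: the same check at a 35% control.** For 35% vs 20%, the weak end of the stated rates, power is 68% and 64% on the two matched readings. The conclusion therefore does not reach the 20% end at the design control rate either.

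**The case against.** Three stronger readings are tempting, and the documents support none of them.

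First, a reader might infer that 13.5% lies outside everything C.6 hypothesised. The 15-20% rates are tied to a 35% start. Against 30%, 13.5% is a 55% relative reduction, inside 40-60%, and C.6 says so in the same sentence. The difference of 16.5 points is also inside the 15-20 points implied by 35% falling to 15-20%.

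Second, a reader might infer that an effect of the design's size becomes a coin toss at a 30% control. The roughly 50% power belongs to 30% vs 18%, a 40% reduction of 12 points. The design case, 35% vs 18%, is a 49% reduction of 17 points. Holding 49% at a 30% control means about 15.4%, with power of about 71% when matched to 35% vs 18% (59-76% across VIF and R, and VIF only). Holding 17 points means 13%, with power of about 85%.

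Third, a reader might infer that 35% is unrealistic because A.1 quotes "up to 33% in nursing home long-term care". That is a prevalence, whereas C.6 concerns new delirium during an acute illness. The comparison does not settle the control rate. The 30% scenario is relevant because C.6 raises it.

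The sponsor can also say that giving the detectable rate already discloses the sensitivity, that C.9 concedes a limited sample size, and that the logistic model in C.7 uses no continuity correction. Without the correction and with VIF only, 30% vs 15% has about 82% power, so the middle of the range is borderline. The lower end is not: 30% vs 18% has 62% on that reading and 68% with no adjustment at all. Disclosing the detectable rate is to the sponsor's credit, but the concluding sentence then ignores it.

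**Conclusion.** The concern holds as a limit on the conclusion, not on the calculation. If usual care is 30%, 150 per group gives 80% power only from about a 53-55% relative reduction upwards. A 50% reduction has about 70-74% power (62-78% across VIF and R, and VIF only), and a 40% reduction about 48-51% (41-56%). The sentence claiming sufficient power for the hypothesised difference is therefore wrong as written for much of the 40-60% range.

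The 80% claim at 35% vs 18% is not refuted by this scenario, and the 13.5% figure reproduces.

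The power figures assume C.6's Figure 1 with continuity correction, no drop-out and an ICC of .01. They are back-calibrated because the use of R and the over-time correlation is not shown, so the ranges should be read alongside the point values. Using the planned 153 per arm instead of 150 changes power by about one point.

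**What to change.** In C.6:

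1. Keep the 13.5% figure and state that it is near the strong end of the 40-60% range.
2. Add power at a 30% control for relative reductions of 40%, 50% and 60% (18%, 15% and 12%). The sponsor should compute these with the adjustment actually used for R and the over-time correlation, and should state that adjustment. The values above are back-calibrated and should not be copied in.
3. Replace the concluding sentence with one limited to the effects covered, for example: power is sufficient for about 35% vs 18% or lower, or for a relative reduction of about 53-55% or more if usual care is 30%. The second threshold should be updated to the sponsor's own calculation.

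A rule that changes how a null result is reported according to the observed control rate should not be added. That would be post hoc power reasoning with an arbitrary cut-off.

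The change is to wording and one short calculation. It needs no extra patients, staff or data; the only downside is a less favourable stated power.

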a sample size of 150 is 1.29 with Cohen's d of 0.41, a moderate effect size. The sample size was also estimated for rate of change of the DI measure over five waves of data (Table 3). Based on data from our previous study, correlations among DI scores over waves (days) averaged 0.5 to 0.6. Thus, ρ is set at .50, .55 and .60. The DI point reduction per day in the intervention group vs. control was posited as $\delta=.24-.27$. This translates to a

DI correlation	n ($\delta=.27$)	δ (n=150)
$\rho=0.6$	117	0.238
$\rho=0.55$	132	0.252
$\rho=0.5$	146	0.266

$$\text{Figure 2. } S_x^2 = \sum (t_i - \bar{t})^2 / 5 = 10/5 = 2; n^* = \frac{2\sigma^2(1-\rho)(z_{\alpha/2} + z_{\beta})^2}{T_n S_x^2 \delta^2}$$

total difference between control and intervention of 1.08 and $d = \delta/\sigma = .35$ (where δ is reduction per day and d is Cohen's d for rate of change). Using the formulas in Figure 2,⁷⁴ with $T_n=5$ time points (baseline and 4 follow-up days), adjusting for reliability and clustering, and with 150 per group, under intent-to-treat (ITT), effect sizes from .238 to .266 are detectable, depending on correlation between waves, translating to a 1 point reduction in DI (medium effect size), with $\alpha=.05$ and $1-\beta=.80$.

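### C.6 applies a reliability factor to Delirium Index figures whose SD, on the plain reading, already contains measurement error, and Table 3 lacks the clustering factor that the text claims

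*Combined protocol and SAP*

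**What the plan says.** Section C.6 first sizes the trial on binary delirium. That passage introduces R=.72, a cluster size of 18, an ICC of .01 and a VIF of 1.17. It does not say which instrument R describes or where the value comes from. The section concludes from the binary figures that "150 subjects per intervention group will provide sufficient power".

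It then turns to the DI. The SD is introduced with the words "power calculations are based on an assumed σ (population pooled standard deviation) of 3.12, using data from our previous study". The effect is the group difference in DI points, and d is that difference divided by the SD. After adjustment for clustering and reliability, the detectable endpoint difference with "a sample size of 150 is 1.29 with Cohen's d of 0.41".

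For the rate of change over five waves, C.6 says: "Based on data from our previous study, correlations among DI scores over waves (days) averaged 0.5 to 0.6". Table 3 gives, for correlations of .60, .55 and .50, n=117, 132 and 146 per group for a difference of .27 points per day, and detectable differences of .238, .252 and .266 at n=150. The text below it says that these figures are adjusted for reliability and clustering.

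**The concern.** Random measurement error does not shrink a mean difference expressed in raw DI points. It widens the spread of the scores. An SD computed from scores that were actually recorded already includes that widening, so a further division by R enters the same error a second time. The slope calculation is exposed in the same way: σ²(1−ρ) is the part of the variance not shared between days, which is where random error sits, and both σ and ρ are taken from earlier DI data.

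At stake is whether the stated DI precision follows from its inputs. The plan posits a total DI difference of 1.08 (.27 × 4 days). As printed, the endpoint comparison cannot detect that with 80% power; without R it nearly can.

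Table 3 raises a second question: whether the two adjustments named in the text are both in the printed numbers.

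**Working it through.** **Inputs, all from C.6.** Two-sided α=.05, so z=1.960; power 80%, so z=0.842; (1.960+0.842)²=7.849. n=150 per group, σ=3.12, VIF=1+17×.01=1.17, R=.72. The DI text does not repeat the value of R; .72 is the only one given.

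**Endpoint: reproducing the plan.** d = √[2 × 7.849/150 × factor], and the difference is d × 3.12.

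| Factor | d | DI points |
|---|---|---|
| none | 0.324 | 1.01 |
| VIF only | 0.350 | 1.09 |
| 1/R only | 0.381 | 1.19 |
| VIF/R = 1.625 | 0.412 | 1.29 |

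Only the last row gives the stated 1.29 and 0.41. One-sided α, 90% power, √R, R² and an ANCOVA factor were also tried, and none gives both numbers.

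**What dividing by R implies.** It is equivalent to using an SD of 3.12/√.72=3.68 while quoting 3.12. The variance is inflated by 1/.72=1.39, that is by 39%.

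**Endpoint without R.** The detectable difference is 1.09 points (d=0.35). At 1.29 points, power with 150 per group is 91%; about 108 per group (92 × 1.17) would give 80%. At the posited 1.08, the standard error is 3.12 × √(2×1.17/150)=0.390, so z=1.08/0.390−1.96=0.81 and power is about 79%. With R retained, the standard error is 0.459, z=0.39 and power is about 65%.

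**Slope: reproducing Table 3.** From Figure 2 with T_n=5 and S_x²=2, n = 2 × 3.12² × (1−ρ) × 7.849/(10 × δ²) × factor = 15.28 × (1−ρ)/δ² × factor. Each cell gives n for δ=.27, then δ at n=150.

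| ρ | none | VIF only | 1/R only | VIF/R | printed |
|---|---|---|---|---|---|
| .60 | 83.9; .202 | 98.1; .218 | 116.5; .238 | 136.3; .257 | 117; .238 |
| .55 | 94.3; .214 | 110.4; .232 | 131.0; .252 | 153.3; .273 | 132; .252 |
| .50 | 104.8; .226 | 122.6; .244 | 145.6; .266 | 170.3; .288 | 146; .266 |

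The printed table matches the column with 1/R only, with n rounded up (131.01 became 132). It contains no VIF.

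**Two changes in Table 3, in opposite directions.** Removing R divides n by 1.39; inserting the VIF multiplies it by 1.17. The net result is 98/110/123 (99/111/123 if rounded up as the table is). If R stays, inserting the VIF gives 136/153/170 (137/154/171 rounded up), which exceeds 150 at ρ=.55 and .50.

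**The case against.** The strongest objection is that the premise is inferred. C.6 calls 3.12 an assumed value based on a previous study and does not say how it was derived. If it is an error-corrected SD, or if R stands for additional rater error expected only in this trial, the endpoint figure of 1.29 is right. Extra error of a smaller amount would fall between: R=.9 gives 1.15 and R=.8 gives 1.22. This stands as a condition. But C.6 mentions no correction and no trial-specific error, so the observed-score reading is the plain one.

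It can also be said that the adjustment is disclosed and 1.29 reproduces exactly. That is true. The fault lies in whether the factor belongs there, not in the multiplication. For the same reason, a reader should not say that the plan's own inputs yield 1.09: R is one of those inputs, and 1.09 appears only once it is removed.

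A reader might infer that R can simply be dropped from Table 3 while its clustering factor is kept. There is none to keep. Dropping R alone leaves 84/94/105 and .202/.214/.226, with no allowance for clustering at all.

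Finally, 1.09 should not be taken as exact. It uses normal quantiles with 17 units and takes ICC=.01 as given. As assumptions outside the plan: t quantiles on 15 degrees of freedom give 1.17, and an ICC of .03 (VIF 1.51) gives 1.24, or 1.33 with t. So a value near 1.29 is plausible for other reasons, but those are not the reasons that C.6 gives.

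**Conclusion.** The point holds, on the assumption that 3.12 and the correlations of .5 to .6 describe observed DI scores. The endpoint figure then overstates the detectable difference: 1.29 (d=0.41) instead of 1.09 (d=0.35), with 91% rather than 80% power at 1.29.

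The missing VIF in Table 3 does not depend on that assumption; the table disagrees with its own description either way. If R goes and the VIF comes in, the table is conservative on balance. If R stays, it is optimistic.

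A reader might infer that the trial is too large or too small. The documents do not support either from this point. The endpoint error is conservative, it concerns only the DI, and C.6 bases 150 per group on binary delirium. Nothing here tests the binary calculation or its use of R.

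All figures are normal approximations with ICC=.01, and apply the same VIF to the slope as to the endpoint.

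**What to change.** In C.6:

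- **Endpoint:** drop R, keep the VIF of 1.17, and restate the detectable difference as 1.09 points (d=0.35).
- **Table 3:** remove R and insert the missing VIF, giving n=98/110/123 for δ=.27 and δ=.218/.232/.244 at n=150, with the rounding rule stated. Amend the sentence on adjustments to match.
- **Alternative:** if 3.12 is meant as an error-free SD, or R as extra error specific to this trial, say so and give the source of both. The endpoint 1.29 then stands, but Table 3 must carry both factors: n=136/153/170 and δ=.257/.273/.288. The claim about what 150 per group can detect must be changed accordingly.

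The cost is a few restated numbers and one or two sentences. Enrolment, conduct and analysis do not change.

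### Table 3 for the Delirium Index slope leaves out the clustering inflation that C.6 says it includes, so 150 per group is short of 80% power at a correlation of 0.55 or below

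*Combined protocol and SAP*

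**What the plan says.** Section C.6 (Power and effect size) opens by saying that the power calculations for both the binary and the continuous delirium outcome allow for clustering by unit. It gives a reliability R of 0.72, a cluster size of 18, an ICC of 0.01 and "variance inflation factor (VIF)=1+(cluster size-1)*ICC=1.17".

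Two calculations follow for the DI, both using "an assumed σ (population pooled standard deviation) of 3.12".

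- **Endpoint difference.** It is introduced with "Adjusting for clustering and reliability, the detectable endpoint difference with" 150 per group and put at 1.29 points, d=0.41.
- **Slope over five daily waves (Table 3, Figure 2).** The plan reports that "correlations among DI scores over waves (days) averaged 0.5 to 0.6" in the earlier study and therefore uses 0.50, 0.55 and 0.60. Table 3 gives n = 117, 132 and 146 per group for a slope difference of 0.27 at correlations of 0.60, 0.55 and 0.50. The slopes detectable with 150 per group are 0.238, 0.252 and 0.266. The text says of these: "adjusting for reliability and clustering, and with 150 per group, under intent-to-treat (ITT), effect sizes from .238 to .266 are detectable".

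**The concern.** Figure 2 as printed contains neither R nor the variance inflation factor, so both adjustments must have been applied to its result afterwards. The Table 3 values look too small for that.

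Table 3 shows a requirement below 150 across the whole range of correlations seen in the sponsor's own data, and so supports the statement that 150 per group is enough for the DI slope. If clustering was left out, that holds only near the top of the range. The DI slope is a planned Aim 1 analysis (C.7) in a trial that randomizes only 17 units (C.3). A reader faced with a null DI result needs to know the power the trial actually had.

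**Working it through.** **Inputs, all from C.6.** σ = 3.12; Tn = 5; Sx² = 2; δ = 0.27; ρ = 0.60, 0.55, 0.50; R = 0.72; VIF = 1 + 17 × 0.01 = 1.17; two-sided α = 0.05 (Figure 2 uses the α/2 quantile); power 0.80. So z(α/2) + z(β) = 1.960 + 0.842 = 2.8016, and its square is 7.849.

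**Step 1: Figure 2 unadjusted.** n* = 2 × 3.12² × (1 − ρ) × 7.849 / (5 × 2 × 0.27²) = 83.85, 94.33, 104.81.

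**Step 2: which adjustment gives Table 3?** The detectable slope at 150 is 0.27 × √(n/150), with n unrounded.

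| Adjustment | n at ρ = 0.60 / 0.55 / 0.50 | Detectable slope at 150 |
|---|---|---|
| None | 84 / 95 / 105 | 0.202 / 0.214 / 0.226 |
| × 1.17 only | 99 / 111 / 123 | 0.218 / 0.232 / 0.244 |
| ÷ 0.72 only | 116.45 / 131.01 / 145.56, i.e. 117 / 132 / 146 | 0.238 / 0.252 / 0.266 |
| × 1.17 ÷ 0.72 | 136.25 / 153.28 / 170.31, i.e. 137 / 154 / 171 | 0.257 / 0.273 / 0.288 |
| **Table 3 as stated** | **117 / 132 / 146** | **0.238 / 0.252 / 0.266** |

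Reliability alone matches all six entries. A one-sided version with both factors gives 108 / 121 / 135, which does not match.

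**Step 3: the plan's own convention, from the endpoint figure.** δ = 3.12 × 2.8016 × √(2k/150), where k is the inflation:

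- k = 1/0.72: 1.19
- k = 1.17: 1.09
- k = 1.17/0.72 = 1.625: 1.287, d = 0.412

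Only the last gives the stated 1.29 and 0.41. The plan's convention is therefore × 1.17 ÷ 0.72, and it was not carried into Table 3.

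**Step 4: power with both adjustments.** Power = Φ(δ / SE − 1.960), with SE² = 2σ²(1 − ρ) × 1.625 / (10 × N).

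- N = 150, δ = 0.27: SE = 0.0919, 0.0974, 0.1027; power 84%, 79%, 75%.
- N = 153 (the planned enrolment per arm, C.1), δ = 0.27: 84.4%, 79.9%, 75.7%.
- N = 150 at the slopes Table 3 calls detectable: each is 2.8016 standard errors without clustering. With it, 2.8016 / √1.17 = 2.590, and Φ(2.590 − 1.960) = Φ(0.630) = 0.736.
- N = 150, δ = 0.24 (the lower end of the posited range): 74.3%, 69.3%, 64.7%.

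**Step 5: break-even.** With both factors and δ = 0.27, 150 per group is enough when 1 − ρ ≤ 0.4 × 150 / 136.25 = 0.440, i.e. ρ of about 0.56 or more.

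**The case against.** **The calculation is supplementary.** C.6 draws its conclusion that 150 per group is sufficient from the binary outcome, and C.7 makes logistic regression on that outcome the primary analysis. Table 3 neither sets the sample size nor feeds into any analysis. This stands, and it limits the consequence to the DI slope.

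**The shortfall is small at 0.55.** With the planned 153 per arm, power there is 79.9%, so nothing of practical weight is lost. This also stands. The material shortfall for a slope of 0.27 lies towards 0.50.

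**1.17 may not be the right inflation for a slope.** A unit effect that is constant over time largely cancels from a within-patient slope, and the documents give no ICC for slopes. The true factor could be lower or higher. This is the strongest point, and it makes 137 / 154 / 171 conditional on 1.17. It does not rescue the table, because the plan offers no such argument, says clustering was adjusted for, and uses a factor of 1.00. At ρ = 0.50 the room is slight: 150 / 145.56 = 1.03, and a factor of 1.10 already needs 145.56 × 1.10 = 160.1, i.e. 161 per group.

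**Another route gives the same table.** Inflation of 1.17/√0.72 with t quantiles also reproduces all six entries. But Figure 2 prints z quantiles, with which that factor gives 116 / 131 / 145 and misses every entry. It also gives about 1.19 for the endpoint difference instead of 1.29.

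**Not all of the low power at 0.24 comes from clustering.** On the reliability-only basis, power at 150 per group is already 80.7%, 76.0% and 71.5%. Omitting the inflation accounts for the remaining 6 to 7 percentage points.

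**Conclusion.** The concern holds. Table 3 is adjusted for reliability only, while the text says reliability and clustering, and the neighbouring endpoint figure uses both. On the plan's stated assumptions, the sample sizes are too low by the factor 1.17 and the detectable slopes too low by √1.17 = 1.08. The claim of 80% power for slopes of 0.238 to 0.266 becomes about 74%.

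For a slope of 0.27, 150 per group is ample at ρ = 0.60, marginally short at 0.55 and clearly short at 0.50 (171 needed, 75% power). Over four days the corrected detectable slopes amount to 1.03, 1.09 and 1.15 DI points. That is still roughly the one point the plan cites, but at the two lower correlations it exceeds the 1.08 points (4 × 0.27) that the plan posits.

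These figures rest on the plan's σ, R and ICC, on 1.17 applying to slopes, and on no dropout. They say nothing against the power of the primary binary comparison.

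**What to change.** Replace the Table 3 entries with n = 137, 154 and 171 and detectable slopes of 0.257, 0.273 and 0.288 at ρ = 0.60, 0.55 and 0.50. Change the range in the sentence to 0.257 to 0.288, and state that 150 per group gives 75% power for a slope of 0.27 at ρ = 0.50. Print R and the inflation factor in Figure 2 so that the table can be reproduced.

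If the sponsor believes a smaller inflation applies to slopes, give the slope ICC and its source and recompute. If no clustering adjustment is intended, say that the table adjusts for reliability only and justify this.

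The cost is one table and one or two sentences. Design, enrolment and conduct do not change; the stated DI slope sensitivity becomes slightly less favourable.

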C. 7. Analysis Aim 1: The primary analysis for the binary outcome will be logistic regression (SAS, PROC GLIMMIX) to test the hypothesis that those assigned to the intervention will have significantly lower rates of delirium compared to those assigned to usual care. The clustering design effect will be modeled. The need for inclusion of covariates resulting from examination of potential sources of bias will be determined. Predicted values from these analyses will be included as covariates in the logistic regression analyses, if necessary. The continuous DI variable will be examined using slope analyses and the repeated measures ANCOVA model in SAS PROC MIXED. This method will allow for more flexible modeling of assumptions, treatment of missing observations and inclusion of all subjects with at least one wave of data, and the inclusion in the analysis of participants who do not complete follow-up assessments (on an ITT basis). Aim 2: The primary analysis for the binary outcome will be logistic regression to test the hypothesis that characteristics of the intervention (e.g., longer visits, components delivered) will be associated with less delirium, using only the intervention group sample and adjusting for covariates as needed to correct for imbalances, since in this case exposure is not assigned. Similar to Aim 1, the clustering design effect will be modeled. The continuous DI variable will be examined using slope analyses and the repeated measures ANCOVA model in SAS PROC MIXED. **Bias and missing data:** We do not expect significant drop-out in this study since it was not observed in our prior study with the 1-month follow-up period. **Attrition bias:** We will use baseline assessment information to compare completers and dropouts with regard to sociodemographics and other covariates. A logit model of attrition will be developed and the predicted values from this model used as a covariate to adjust for differential attrition. **Treatment of missing data:** Using the maximum-likelihood approach we will include baseline data, and we will try to obtain follow-up data from all randomized patients so non-completion will not result in loss to follow-up.

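### C.7 does not name baseline Delirium Index as a covariate in either DI model, the slope test sized in C.6 leaves each arm its own baseline, and Table 3 omits the clustering allowance it claims

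*Combined protocol and SAP*

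**What the plan says.** On the continuous outcome, C.7 (Aim 1) states: "The continuous DI variable will be examined using slope analyses and the repeated measures ANCOVA model in SAS PROC MIXED". It adds that baseline data will enter through maximum likelihood. It does not say whether baseline DI is a covariate, a constrained common start or simply the first response, and it does not say which DI analysis leads.

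C.6 sizes two DI comparisons at 150 per group.

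- **Endpoint.** After allowance for clustering and reliability, the detectable difference with "a sample size of 150 is 1.29 with Cohen's d of 0.41, a moderate effect size".
- **Slope.** Figure 2 uses five "time points (baseline and 4 follow-up days), adjusting for reliability and clustering". Table 3 gives detectable slopes of .266, .252 and .238 per day at correlations of .5, .55 and .6, and 146, 132 and 117 per group for a slope of .27.

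The correlations come from earlier data, in which "correlations among DI scores over waves (days) averaged 0.5 to 0.6". C.6 turns .27 per day into a total difference of 1.08. That is 4 × .27, which takes the arms to start level.

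**The concern.** Baseline DI is collected and, on C.6's figures, predicts later DI well. Neither sizing formula uses it that way. The endpoint figure has no baseline term. The slope formula spends information on estimating a baseline gap between arms that C.6's own effect takes to be zero. C.7 does not settle the matter, because a model with free arm intercepts also includes baseline data, as the first of five outcomes.

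Three things are at stake. With 17 units and about 150 patients per group, and with limited sample size listed as a limitation in C.9, avoidable noise matters. A model left open can be chosen after the data are seen. And a reader cannot tell which analysis the stated detectable differences belong to.

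**Working it through.** **Inputs, all from C.6.** SD of DI 3.12; "assumed reliability (R)=.72; groups (g)=2; cluster size (by unit)=18; intraclass correlation (ICC)=.01"; VIF = 1 + 17 × .01 = 1.17; two-sided α = .05 and 80% power, so z sum = 1.960 + 0.842 = 2.802 and its square is 7.849; n = 150 per group; ρ = .5, .55, .6; days 0 to 4, so Tn × Sx² = 5 × 2 = 10.

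**1. Reproduce the endpoint figure.** √(2 × 3.12² × 7.849 × (1.17/.72) / 150) = 1.287, or d = .41. This is the stated 1.29. It uses VIF and R and has no (1 − ρ²) term.

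**2. Reproduce Table 3.** Figure 2 divided by R alone, at ρ = .5 and a slope of .27: n = 2 × 3.12² × .5 × 7.849 / (10 × .27² × .72) = 145.6, so 146. The detectable slope at n = 150 is .266. The other two rows also match (132 and .252; 117 and .238). Multiplying by the VIF as well gives n = 171/154/137 and slopes of .288/.273/.257, which are not the printed values. So the table carries R but not the VIF. Power at the printed slopes once the VIF is applied: Φ(2.802/√1.17 − 1.960) = Φ(0.63) ≈ 74%.

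**3. What baseline DI adds to the slope.** With equal correlation at all lags, information on the arm difference in slope, in units of 1/{σ²(1 − ρ)}, is:

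- own intercept per arm: Σ(t − 2)² = 10, which is Figure 2;
- level start: Σt² − ρ(Σt)²/(1 + 4ρ) = 30 − 100ρ/(1 + 4ρ) = 13.33/12.81/12.35.

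Taking baseline DI as a covariate and modelling days 1 to 4, with the arm difference proportional to time, gives the same 13.33/12.81/12.35. This needs the arm term to be arm-by-time only. If a separate arm shift is also fitted on days 1 to 4, the slope information is Σ(t − 2.5)² = 5, half of Figure 2's.

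**4. Results at n = 150.** Power = Φ(2.802 × √ratio − 1.960), with 2.802 divided by √1.17 where the VIF applies.

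| | ρ = .5 | ρ = .55 | ρ = .6 |
|---|---|---|---|
| Information ratio | 1.333 | 1.281 | 1.235 |
| Slope printed in Table 3 | .266 | .252 | .238 |
| Power there, R only: free intercept → baseline used | 80 → 90% | 80 → 89% | 80 → 88% |
| Power there, VIF and R: free intercept → baseline used | 74 → 85% | 74 → 83% | 74 → 82% |
| Detectable slope, VIF and R: free intercept → baseline used | .288 → .249 | .273 → .241 | .257 → .232 |
| n per group for .27, VIF and R: free intercept → baseline used | 171 → 128 | 154 → 120 | 137 → 111 |

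**5. Endpoint with baseline DI as covariate.** 1.287 × √(1 − ρ²) = 1.11/1.07/1.03, if the baseline-to-endpoint correlation equals ρ.

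**6. If correlation decays with time (an assumption).** C.6 gives only an average correlation. Under a first-order autoregressive pattern with the same averages, the baseline-to-day-4 correlation is about .22 to .34. The endpoint figure is then 1.287 × √(1 − .22²) ≈ 1.26 down to 1.287 × √(1 − .34²) ≈ 1.21. Slope power at the printed slopes, with the VIF, goes from about 46/45/44% to 67/64/60%: a larger gain from a lower start.

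**The case against.** **The planned ANCOVA probably already uses baseline DI.** If so, that analysis loses nothing. This stands. A reader might infer from step 5 that the trial gives up as much as 14 points of power on the endpoint (80% against 94% at 1.29, ρ = .6). The documents do not support that, because C.7 lists no unadjusted endpoint test. The 1.29 merely understates what a baseline-adjusted ANCOVA could detect.

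**Figure 2 is a planning formula, not the analysis model.** This also stands. C.7 is silent on arm intercepts, so the text shows that the slope model is unspecified, not that free intercepts will be fitted.

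**Free intercepts are defensible here.** Units are assigned before enrolment (C.3), and patients are found partly through referral by unit staff (C.2), so baseline DI could truly differ between arms. Forcing a common start could turn such a difference into an apparent effect. The blinded research assistant (C.8), the 99.1% capture rate and the 3% refusal rate (C.2) limit this risk without removing it. It is a good reason not to make the common-baseline slope the lead model.

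**The VIF may not belong in a slope test.** A unit effect that is constant over time cancels from a free-intercept slope. That is arguable, but C.6 says clustering was allowed for, and units may also differ in rate of change. On that view the free-intercept slope keeps 80% power. Using baseline DI gives information 30 − 100(ρ + .17)/{(1 − ρ) + 5(ρ + .17)} = 12.60/12.22/11.88 against 10, with .17 = 17 × .01. Power is then about 88/87/86%, so a gain remains.

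**Conclusion.** The point holds as a gap in specification and an inconsistency in sizing. Neither DI model names baseline DI, and no main DI contrast is named. Measured against the slope test that C.6 sizes, using baseline DI is worth about 8 to 10 points of power at the printed slopes. With the VIF that C.6 says it applied, the test as sized falls to about 74% at those slopes, and using baseline DI returns it to 82–85%.

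These figures rest on C.6's SD, reliability and ICC, on equal correlation at every lag, and on arms that start level. Under decaying correlation the slope gain grows but power stays below 80% either way, and the endpoint gain nearly vanishes.

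A reader might also infer that the trial's main conclusion is at risk. The documents do not support this: C.7 attaches its primary-analysis wording to the binary delirium outcome, and C.6 rests its statement that 150 per group is sufficient on that outcome. The error in 1.29 is conservative. The error in Table 3 is optimistic.

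**What to change.** **In C.7:**

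- Name pre-intervention baseline DI as a covariate in both DI models, with unit as a random effect.
- For the slope model, state that the arm effect is the arm-by-time term counted from baseline, with no separate arm shift.
- Name one main DI contrast.
- Report the common-baseline slope and the free-intercept slope as sensitivity analyses, because patients are recruited after units are assigned.
- Define baseline by the same timing rule in both arms. DI is taken on weekdays only (C.5) while the nursing assistant visits seven days a week (C.4), so some first scores may follow a first visit.

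**In C.6:** restate the endpoint and Table 3 detectable differences for those models, with the VIF applied and the correlation pattern stated. If the VIF is judged not to apply to slopes, say so and remove the claim that clustering was allowed for.

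**Cost:** a few sentences and a change to the model statement, with no new patients, visits or staff. There are two downsides. Covariate adjustment corrects a baseline imbalance between arms only in part, which is why the free-intercept slope is kept. Patients without a pre-intervention DI would drop out of a plain covariate model, so they need likelihood-based handling.
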